#### 11.4. Search Criteria for TEAEs of Special Interest

AESI Category	Search Criteria
Anaphylactic reactions	Narrow SMQ for anaphylactic reaction
Systemic hypersensitivity reactions	Narrow SMQ for hypersensitivity Note: manual adjudication of relevant PTs will be required by the study medical monitor, before database lock
Helminthic infections	HLT = Cestode infections HLT = Helminthic infections NEC HLT = Nematode infections HLT = Trematode infections
Any severe type of conjunctivitis or blepharitis	Broad CMQ conjunctivitis PTs 1. Conjunctivitis 2. Conjunctivitis allergic 3. Conjunctivitis bacterial 4. Conjunctivitis viral 5. Atopic keratoconjunctivitis 6. Blepharitis 7. Dry eye 8. Eye irritation 9. Eye pruritus 10. Lacrimation increased 11. Eye discharge 12. Foreign body sensation in eyes 13. Photophobia 14. Ocular hyperaemia 15. Conjunctival hyperaemia 16. Xerophthalmia Blepharitis PTs 1. Blepharitis allergic 2. Bacterial blepharitis AND

AESI Category	Search Criteria
	Serious AE= "Yes" OR Severity= "severe"
Keratitis	Narrow SMQ for corneal disorders
Clinically symptomatic eosinophilia (or eosinophilia associated with clinical symptoms)	HLT = Eosinophilic disorders PT = Eosinophil count increased Note: manual adjudication of relevant PTs will be required by the study medical monitor, before database lock.
Severe injection site reactions	HLT=Injection Site Reactions AND Serious AE= "Yes" OR Severity= "severe"
Herpes simplex infection	HLT=Herpes viral infections
Arthralgia	PT=Arthralgia

Note: The search criteria are meant to assist the process of identification of TEAE of Special Interest/TEAE Syndrome. However, since these criteria might not be exhaustive in some cases or may not be specific in other cases, an additional blinded review of all PTs in the database may be performed by the Medical monitor, based on medical judgement, to identify any TEAE of Special Interest/TEAE Syndrome that might have been missed by the criteria or to identify any TEAE may be inaccurately assigned as AESI by the algorithmic search.

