3.2.3.2. Risks

As of 28 March 2020, over 8000 subjects have been enrolled into the dupilumab development program for the indications of AD, asthma, chronic rhinosinusitis with nasal polyps (CRSwNP), grass allergy, peanut allergy, bullous pemphigoid, and EoE (Investigator's Brochure Version 14).

Based upon currently available data, 1 important identified risk, “Systemic Hypersensitivity (including those events associated with immunogenicity),” has been established. One serious case each of serum sickness and serum sickness-like reaction (both associated with high anti-drug antibody [ADA] titers) were reported in adult AD studies, however none were seen in the asthma development program. Additionally, there has been one report of anaphylaxis considered related to study drug by the Investigator in an asthma study. Based on the review of post-marketing data, signals of anaphylactic reaction and angioedema were confirmed and considered as adverse drug reactions (ADRs).

A higher incidence of Injection Site reactions (ISRs) has been observed in the dupilumab-treated subjects, consistent with the SC injection of a protein biologic. Most ISRs were mild to moderate in intensity, and less than 2% were severe or led to treatment discontinuation. The proportion of patients experiencing ISRs diminished over time during the treatment period.

Conjunctivitis, Conjunctivitis Allergic, Conjunctivitis Bacterial, Blepharitis, Dry Eye, Eye Pruritus, Herpes Simplex (primarily mucocutaneous in nature), and Oral Herpes have been identified as adverse drug reactions for the AD indication. There was no increase in incidence of these events observed in the completed asthma study. Conjunctivitis was also observed in the completed CRSwNP studies but with lower incidence than in the AD studies and without keratitis or increase in other ophthalmic events. Most events were mild in intensity and transient in nature, and did not necessitate treatment discontinuation. Based on the post-marketing safety data, events of angioedema, arthralgia, keratitis and ulcerative keratitis are now considered as ADRs.

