9.4.3. Other Events that Require Accelerated Reporting to Sponsor

The following events also require reporting to the sponsor (or designee) within 24 hours of learning of the event:

Symptomatic Overdose of Study Drug: Accidental or intentional overdose of at least 2 times the intended dose of study drug within the intended therapeutic window, if associated with an AE.

Pregnancy: Although pregnancy is not considered an AE, it is the responsibility of the investigator to report to the sponsor (or designee), within 24 hours of identification, any pregnancy occurring in a female study patient, during the study or within 12 weeks of the last dose of study drug. Any complication of pregnancy affecting a female study patient and/or fetus and/or newborn that meets the SAE criteria must be reported as an SAE. Outcome for all pregnancies should be reported to the sponsor.

Adverse Events of Special Interest: All AESI, serious and non-serious, must be reported within 24 hours of identification using the same reporting process as for SAE reporting, per Section 9.4.2. Adverse events of special interest for this study include the following:

- Anaphylactic reactions
- Systemic hypersensitivity reactions
- Helminthic infections
- Any severe type of conjunctivitis or blepharitis
- Keratitis
- Clinically symptomatic eosinophilia (or eosinophilia associated with clinical symptoms)
- Severe injection site reactions
- Herpes simplex infection

- Arthralgia

Refer to the study manual for the procedures to be followed.

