#### 5.7.1. Adverse Events

The number and proportion of patients reporting TEAEs will be summarized for Part B week 24 treatment period, Part C extended active treatment period, and follow-up period, as described in Section 3.2.

- For the summary of Part B treatment period, TEAEs with onset date during the Part B treatment period will be included. TEAEs that had an onset during the Part B treatment period and continued afterwards into Part C treatment period or the follow-up period will be counted only once as TEAEs during the Part B treatment period.
- For the summary of Part C extended treatment period, TEAEs with onset during the Part C extended treatment period will be included. TEAEs that had an onset during the Part C treatment period and continued afterwards into the follow-up period will be counted only once as TEAEs during the Part C extended treatment period.
- For the follow-up period, TEAEs with onset during the follow-up period will be included.

AE incidence tables will be presented by treatment group for the SAF as well as for selected subgroups. TEAE summaries will present the number (n) and percentage (%) of subjects experiencing an TEAE by SOC and PT, sorted by decreasing frequency of SOC and PT for the dupilumab treatment group. Multiple occurrences of AEs of the same PT (or SOC) in the same subject will be counted only once for that PT (or SOC). For tables presenting severity of events, the worst severity will be chosen for subjects with multiple instances of the same event. The denominator for computation of percentage is the number of patients in each treatment group for the corresponding analysis period as specified in Section 3.2.

An overall summary of TEAEs will be provided with number and proportions of patients with any:

- TEAE
- Serious TEAE
- TEAE of special interest (AESI)
- TEAE leading to death
- TEAE leading to permanent treatment discontinuation

Detailed summaries of TEAEs will include:

- TEAEs
  - TEAEs by SOC/PT
  - TEAEs by PT
  - TEAEs by SOC/PT with incidence of PT  $\geq 5\%$  in any treatment group
  - TEAEs by severity by SOC/PT
  - TEAEs related to study medication as assessed by the investigator by SOC/PT
  - TEAE of special interest by category (see Section 11.4)
- Serious TEAEs:
  - Serious TEAEs by SOC/PT
  - Serious TEAEs related to study medication as assessed by the investigator by SOC/PT
- TEAEs leading to permanent discontinuation of study treatment by SOC/PT
- Fatal TEAEs by SOC/PT

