**5.10.2. Immunogenicity and Safety/Efficacy**

Potential association between ADA responses and safety may be explored with a primary focus on the following safety events during the TEAE period:

- TEAE
- Serious TEAE
- TEAE leading to permanent treatment discontinuation

- Injection site reaction (HLT=' Injection site reaction')
- Hypersensitivity (AESI category 'Hypersensitivity')
- Anaphylaxis (SMQ: Anaphylactic Reaction [Narrow])

Potential association between ADA responses and impact on individual patient efficacy endpoint profiles may be explored (e.g. scatter plot or spaghetti plot).

The safety and efficacy analyses mentioned above will be conducted using the following ADA response categories:

- ADA negative patients, that is patients with pre-existing immunoreactivity or negative in the ADA assay at all time points.
- ADA positive patients, that is patients with treatment-emergent or treatment-boosted response.
- Patients with persistent treatment-emergent ADA response
- NAb positive patients, that is ADA positive patients who were positive in the NAb assay at any time point analyzed.
- Maximum post-first dose titer in treatment-emergent or treatment-boosted ADA positive patients:
  - Low (titer <1,000)
  - Moderate ( $1,000 \leq \text{titer} \leq 10,000$ )
  - High (titer >10,000)

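### SAP 5.7.1 plans no any-severity grouped patient count by arm for injection site reactions or for conjunctivitis/blepharitis

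*SAP*

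**What the plan says.** **Definitions.** Protocol 9.4.3 lists nine categories of adverse events of special interest (AESIs). Two are limited by severity in their names: severe injection site reactions, and "Any severe type of conjunctivitis or blepharitis". SAP 4.5.1 repeats the list. SAP 11.4 gives the searches. For ISRs it is "HLT=Injection Site Reactions AND Serious AE= 'Yes' OR Severity= 'severe". For the eye events it is a list of 16 conjunctivitis and 2 blepharitis preferred terms (PTs), combined with "Serious AE= 'Yes' OR Severity= 'severe". The other seven searches carry no severity filter.

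**Outputs.** SAP 5.7.1 plans TEAE tables by system organ class (SOC) and PT, by PT, by SOC/PT where a PT reaches 5% in any treatment group, by severity, and by relatedness. These give the number and percentage of patients per treatment group. SAP section 5 adds a combined dupilumab column for safety. The AESI outputs are a table by category and Kaplan-Meier time to first event by category, both resting on the 11.4 searches.

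**What is known of these harms.** Protocol 3.2.3.2 reports more ISRs on dupilumab and adds: "Most ISRs were mild to moderate in intensity, and less than 2% were severe or led to treatment discontinuation". It lists conjunctivitis, blepharitis and related eye terms as adverse drug reactions for the atopic dermatitis indication, and says: "Most events were mild in intensity and transient in nature, and did not necessitate treatment discontinuation".

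**The one unfiltered grouping.** SAP 5.10.2 names "Injection site reaction (HLT=' Injection site reaction" with no severity condition, for the analysis of anti-drug antibodies (ADA) and safety.

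**The concern.** The severe-only categories serve rapid reporting. They do not describe harms that are expected to be mostly mild or moderate. Once an event falls outside the filter, the only routine place for it is a PT row, and no planned table joins those rows into a count of patients.

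For ISRs the missing count is of particular interest. Protocol 7.1 has every patient injected weekly, with placebo injections between the Q2W doses, so the number of injections is the same in all three arms of Part B. A comparison of ISR incidence across QW, Q2W and placebo is therefore not disturbed by injection frequency. Protocol 9.5.1 also defines a dedicated mild/moderate/severe scale for ISRs, yet no grouped output by arm uses its lower two levels.

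**Working it through.** The documents give no figure to reproduce here. The check is a reading of every planned output, followed by an illustration.

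**1. Which outputs could give an any-severity grouped count by arm?**

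| Output | Any severity? | Grouped to distinct patients? | By arm? |
|---|---|---|---|
| SAP 5.7.1 SOC/PT, PT, severity and relatedness tables | Yes (relatedness table: related events only) | No, by PT (the SOC row also pools other terms) | Yes |
| SAP 5.7.1 AESI by category | No, serious or severe | Yes | Yes |
| SAP 5.7.1 Kaplan-Meier time to first AESI | No, serious or severe | Yes | Yes |
| SAP 5.10.2 ISR at high level term (HLT) | Yes | Yes | No, by ADA category |

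The 5.10.2 analysis is optional in its wording. Under SAP 5.10 it runs only if treatment-emergent ADA exceeds 5% in some group. No any-severity conjunctivitis grouping appears anywhere. The note closing 11.4 lets the medical monitor correct AESI assignments in a blinded review, but it creates no unfiltered group.

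**2. Can the PT rows be combined?** SAP 5.7.1 counts a patient once within each PT or SOC, so one patient may stand in several PT rows. The number of distinct patients lies between the largest PT count and the sum of the counts. With assumed PT counts of 7, 5 and 4, it could be anything from 7 to 7 + 5 + 4 = 16.

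Splitting also affects the 5% table. The threshold is 0.05 × 70 = 3.5 patients, so a PT with 3 patients (3/70 = 4.3%) is left out. Four PTs with three different patients each (assumed) would be 12/70 = 17% of an arm, with no PT reaching 5%. They would still appear in the full SOC/PT table.

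**3. Illustration for ISRs.** Inputs are 70 per arm (SAP 2.1), a severe share of 2% (the upper bound in Protocol 3.2.3.2, read as a share of ISRs), and an any-severity incidence p of 10%, 20% or 40%. The incidence is assumed, because the documents give none.

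With one ISR per affected patient:
- Any ISR: 70 × p = 7, 14, 28 patients.
- Expected in the severe row: 70 × p × 0.02 = 0.14, 0.28, 0.56.
- Chance of at least one patient in that row: 1 − (1 − 0.02p)^70 = 13%, 24%, 43%.

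With five independent ISRs per affected patient (also assumed), the chance that such a patient has a severe one is 1 − 0.98^5 = 9.6%:
- Expected in the severe row: 70 × p × 0.096 = 0.67, 1.35, 2.7.
- Chance of at least one patient: about 49% at p = 10% and 94% at p = 40%.

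No such calculation is possible for conjunctivitis/blepharitis, because the protocol gives no severe share for it.

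**The case against.** **The events are reported.** A reader might infer that the plan never shows how many patients had these reactions. The documents do not support that. SAP 5.7.1 gives each PT per arm at every severity, with worst severity per patient, and so gives a QW, Q2W and placebo comparison for each PT. Only the pooled count of distinct patients is absent.

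**The filter is not an error.** It reproduces the protocol's own AESI names, and the protocol's amendment history attributes revisions of the AESI definitions to regulatory feedback. This stands, and the definitions should not change.

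**Readers would not be misled.** A reader might also infer that a near-empty AESI row would be taken as absence of a signal. Both rows are labelled severe, and the any-severity tables belong to the same set of outputs, so that inference is not supported.

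**The size is uncertain.** The incidences are assumed. The figure of under 2% comes from the wider dupilumab programme and also includes discontinuations. The result moves several-fold with the number of ISRs per patient. Conjunctivitis and blepharitis are listed as reactions for atopic dermatitis; the protocol reports no increase in the completed asthma study and a lower conjunctivitis incidence in nasal polyps. All of this stands and limits the arithmetic to an illustration.

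**Safety is descriptive.** No hypothesis or alpha is affected, and the pooling could be done later. That lowers the weight of the point. It does not remove the advantage of fixing the grouping before unblinding.

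**Conclusion.** The gap is real but modest. The routine safety outputs contain no any-severity patient-level incidence by arm for ISRs or for conjunctivitis/blepharitis, and the planned PT rows cannot be turned into one. This rests on the text of SAP 5.7.1, 5.10 and 11.4 and needs no numerical assumption.

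The size is known only by illustration. Under 10% to 40% incidence, one ISR per affected patient and 2% severe, 7 to 28 affected patients per arm correspond to 0.14 to 0.56 expected in the severe row. With five ISRs per patient, the expectation is 0.67 to 2.7. Either way the severe row holds a small fraction of affected patients, but the documents do not establish that it would be empty. Efficacy conclusions and type I error are untouched. This is a cheap improvement in safety reporting.

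**What to change.** Keep the AESI definitions in Protocol 9.4.3 and SAP 11.4. Add to SAP 5.7.1, for Part B and for Part C:

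- the number and percentage of patients with any ISR, using the HLT already named in SAP 5.10.2;
- the number and percentage with any conjunctivitis/blepharitis term, using the PT list already in SAP 11.4. That list is broad and includes terms such as dry eye and photophobia, so label the row accordingly.

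Present each by treatment group and for combined dupilumab, count each patient once, split by worst severity, and add a Kaplan-Meier display of time to first event. Place the rows beside the severe AESI rows.

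While editing, put brackets in the two 11.4 searches so that the severity condition reads as grouping term AND (serious OR severe). Without brackets, the string could be programmed to pick up any severe event.

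The cost is a short change of wording and two extra tables with their plots, from data already coded. No data collection or clinical rule changes. The only downside is slightly more output.

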### 11.5. EoE Histology Scoring System (EoEHSS) Feature Evaluation Per Collins et al. 2017

Feature	Grade Score	Stage Score
Eosinophilic inflammation (EI)	0 = intraepithelial eosinophils not present 1 = PEC <15/HPF 2 = PEC 15-59/HPF 3 = PEC >60/HPF	0 = intraepithelial eosinophils 0-14/HPF, 1 = PEC ≥15/HPF in <33% of HPFs 2 = PEC ≥15/HPF in 33-66% of HPFs 3 = PEC ≥15/HPF in >66% of HPFs
Basal zone hyperplasia (BZH)	0 = BZH not present 1 = basal zone occupies >15% but <33% of total epithelial thickness 2 = basal zone occupies 33-66% of total epithelial thickness 3 = basal zone occupies >66% of total epithelial thickness	0 = BZH not present 1 = BZH (any grade >0) in <33% of epithelium 2 = BZH (any grade >0) in 33-66% of epithelium 3 = BZH (any grade >0) in >66% of epithelium
Eosinophil abscess (EA)	0 = groups or aggregates of eosinophils not present 1 = group of 4-9 eosinophils 2 = group of 10-20 eosinophils 3 = group of >20 eosinophils	0 = groups or aggregates of eosinophils not present 1 = EA (any grade >0) in <33% of epithelium 2 = EA (any grade >0) in 33-66% of epithelium 3 = EA (any grade >0) in > 66% of epithelium
Surface layering (SL)	0 = absent SL (fewer than 3 aligned eosinophils) 1 = SL of 3-4 eosinophils 2 = SL of 5-10 eosinophils 3 = SL of >10 eosinophils	0 = absent SL 1 = SL (any grade >0) in <33% of epithelium 2 = SL (any grade >0) in 33-66% of epithelium 3 = SL (any grade >0) in >66% of epithelium.
Dilated intercellular spaces (DIS)	0 = DIS not seen at any magnification 1 = intercellular bridges in DIS visible at 400X magnification only 2 = intercellular bridges in DIS visible at 200X magnification 3 = intercellular bridges in DIS visible at 100X magnification or lower	0 = DIS not seen at any magnification 1 = DIS (any grade >0) in <33% of epithelium 2 = DIS (any grade >0) in 33-66% of epithelium 3 = DIS (any grade >0) in >66% of epithelium
Surface epithelial alteration (SEA)	0 = SEA not present 1 = SEA without eosinophils 2 = SEA with any eosinophils 3 = shed altered surface epithelium admixed with numerous eosinophils consistent with exudate	0 = SEA not present 1 = SEA (any grade >0) in <33% of epithelium 2 = SEA (any grade >0) in 33-66% of epithelium 3 = SEA (any grade >0) in >66% of epithelium

Feature	Grade Score	Stage Score
Dyskeratotic epithelial cells (DEC)	0 = DEC not present 1 = 1 DEC/HPF 2 = 2-5 DEC/HPF 3 = >5 DEC/HPF	0 = DEC not present 1 = DEC (any grade >0) in <33% of epithelium 2 = DEC (any grade >0) in 33-66% of epithelium 3 = DEC (any grade >0) in >66% of epithelium
Lamina propria fibrosis (LPF)	0 = LPF not present 1 = fibers are cohesive and interfiber spaces cannot be demarcated 2 = fiber diameter equals the diameter of a basal cell nucleus 3 = fiber diameter exceeds the diameter of a basal cell nucleus	0 = LPF not present 1 = LPF (any grade >0) in <33% of lamina propria 2 = LPF (any grade >0) in 33-66% of lamina propria 3 = LPF (any grade >0) in >66% of lamina propria

PEC = peak eosinophil count (quantity of eosinophils in the most inflamed high power field)

### 11.6. Gene Lists Comprising Each Transcriptome Endpoint

EoE diagnostic panel	Type 2 inflammation signature
CDH26 CDH20 CLDN10 CTNNA1 DSG1 CHL1 CXCL6 CCL26 CXCL1 IL8 IL5 IL13 CCR3 CLC IL5RA CRISP2 FLG UPK1A SPINK7 CRISP3 ACPP UPK1B CA2 PHLDB2 MUC4 GCNT3 EPPK1 ZNF365 CITED2 ARG1 ALOX12 IGJ TNFAIP6 CFB HRH1 CFI APOBEC3A MMP12 CD200R1 HPGDS FCGR3A FCGR3B RUNX2 ALOX15 GRK5 SAMSN1 PMCH SLC16A6 KCNJ2 ANO1 SLC26A4 TPSAB1 TPSB2 CPA3 CMA1 NEFM NEFL PNLIPRP3 ENDOU	IL4 IL13 [REDACTED] IL4R IL5 [REDACTED] TSLP [REDACTED] [REDACTED] [REDACTED] [REDACTED] [REDACTED] CCL26 [REDACTED] [REDACTED] [REDACTED] CCR3 [REDACTED] [REDACTED] [REDACTED] [REDACTED] CLC ALOX15 [REDACTED] [REDACTED] POSTN [REDACTED] CMA1 TPSAB1 HRH1 [REDACTED] [REDACTED] ARG1 [REDACTED]

EoE diagnostic panel	Type 2 inflammation signature
CDA EML1 SUSD2 GPR160 TSPAN12 LRRRC31 GLDC GYS2 IGFL1 MT1M CRYM UBD GRPEL2 RTP4 ACTG2 CTSC POSTN KRT23 COL8A2 IL32 IL4 MSRB3 CCL8 EPX EPB41L3 SYNPO2 COL1A2 TRIM2 SYNPO2L NCAM1 F3 TSLP H19 FKBP5 SLAMF7 PTGFRN	

### 11.8. EQ-5D-3L Utility Index scoring (UK Tariff)

**Table 9: Coefficients of Regression Model Based on UK population**

Variable (Xi)	Definition	Coefficients in UK model (βi)
Constant	At least one level at 2 or 3	0.081
Mobility		
Level 2	Mobility at level 2	0.069
Level 3	Mobility at level 3	0.314
Self-care (S-C)		
Level 2	S-C at level 2	0.104
Level 3	S-C at level 3	0.214
Usual activities (UA)		
Level 2	UA at level 2	0.036
Level 3	UA at level 3	0.094
Pain or discomfort (P/D)		
Level 2	P/D at level 2	0.123
Level 3	P/D at level 3	0.386
Anxiety or depression (A/D)		
Level 2	A/D at level 2	0.071
Level 3	A/D at level 3	0.236
N3	Any dimension at level 3	0.269

*Model for Utility index score:*

$$\text{utility index score} = 1 - \sum_{i=1}^{12} (\beta_i * X_i),$$

where Xi is a dummy variable with value 1 if the definition for this variable is met and 0 otherwise (e.g X1 = 1 if the patient has at least one level at 2 or 3 from 5 dimensions, otherwise X1 = 0).

For example, if the patient only have mobility at level 2 (i.e. some problems in mobility) and others are level 1 (i.e. no problem on the other 4 dimensions), then only “At least one level at 2 or 3” and “Mobility at level 2” are met and the utility index score= $1-(1*0.081+1*0.069)=0.85$ .

SAS code

```
data EUROQOL; set temp;
profil= (10000*eqq1cd)+(1000*eqq2cd)+(100*eqq3cd)+(10*eqq4cd)+eqq5cd;
eq5d=1;
*****Mobility*****;
if eqq1cd=2 then eq5d=eq5d-0.069;
if eqq1cd=3 then eq5d=eq5d-0.314;
*****Self-care*****;
if eqq2cd=2 then eq5d=eq5d-0.104;
if eqq2cd=3 then eq5d=eq5d-0.214;
*****Usual activities*****;
if eqq3cd=2 then eq5d=eq5d-0.036;
if eqq3cd=3 then eq5d=eq5d-0.094;
*****Pain/discomfort*****;
if eqq4cd=2 then eq5d=eq5d-0.123;
if eqq4cd=3 then eq5d=eq5d-0.386;
*****Anxiety/depression*****;
if eqq5cd=2 then eq5d=eq5d-0.071;
if eqq5cd=3 then eq5d=eq5d-0.236;
if (eqq1cd ne 1 or eqq2cd ne 1 or eqq3cd ne 1 or eqq4cd ne 1 or eqq5cd ne 1)
then eq5d=eq5d-0.081;
if (eqq1cd=3 or eqq2cd=3 or eqq3cd=3 or eqq4cd=3 or eqq5cd=3)
then eq5d=eq5d-0.269;
if (eqq1cd=. or eqq2cd=. or eqq3cd=. or eqq4cd=. or eqq5cd=.)
then eq5d=.;

run;
```

Signature Page for VV-RIM-00168730 v1.0

ESig Approval	[Redacted] 00
---------------	---------------

ESig Approval	[Redacted] 00
---------------	---------------

ESig Approval	[Redacted] -2021 15:13:19 GMT+0000
---------------	---------------------------------------

Signature Page for VV-RIM-00168730 v1.0 Approved
